## **6.0 Data Banking N/A**

## **7.0 Sharing of Results with Participants**

- 7.1 We will not share results with participants.

## **8.0 Study Duration**

- 8.1 Individual participants will participate for approximately 2 hours over a 5 month time frame.

We will enroll all participants within 6 months and anticipate all study procedures and data analysis will be completed within 24 months.

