## 3.0 Study Endpoints/Events/Outcomes

3.1 Primary Endpoint/Event/Outcome:

Interviews: Identify themes to develop 1) a cancer-specific, multi-tiered activity/trip classification system to organize cancer treatment-related activities and trips in the app; and 2) user stories to describe what the users want to do with the proposed app.

Follow-up survey: Overall satisfaction with proposed system design will be measured using a 5-point Likert scale from not at all satisfied to very satisfied. The primary endpoint will be the proportion of participants who report an overall satisfaction score of 4.0 or above.

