## **SOCIAL PROTOCOL (HRP-580)**

**PROTOCOL TITLE:** App-Assisted Day Reconstruction to Reduce Treatment Burden and Logistic Toxicity in Cancer Patients – Aim 1

**VERSION DATE:** 01/05/2023

treatment for cancer. After recruitment and obtaining informed consent, an interviewer trained by Drs. [name] and [name] will use a semi-structured guide including open-ended questions. Following review by the research team and CAB, the interview guide will be assessed after the first five interviews for any necessary changes. If significant edits are made, those interviews will be treated as pilot data and left out of the analysis. Interviews will be digitally recorded and transcribed verbatim.

After the system design, the 20 interview participants will be sent a follow-up survey (approximately 15 minutes) online via REDCap or paper via mail to review the user interface sketches and app function narratives. Participants will be asked to provide open-ended feedback as well as their satisfaction ratings with each user interface sketch and app function narrative using a 5-point Likert scale from not at all satisfied to very satisfied. For each participant, the satisfaction ratings will be averaged to derive an overall satisfaction score.

- 5.3 Follow-Up: Survey data will be collected.
- 5.4 Individually Identifiable Health Information: We will obtain written HIPAA agreement from participants and authorization to communicate via email if that is the participant's preference.

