## 11.0 Number of Participants

11.1 Number of Participants to be Consented: up to 30, 20 participants to complete interviews

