## 13.0 Withdrawal of Participants

13.1 Withdrawal Circumstances: No participant will be withdrawn from the study against their will. Participants will only be withdrawn from the study if they ask to withdraw or become too ill or die prior to completing the study. If participants become too ill,

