## SOCIAL PROTOCOL (HRP-580)

PROTOCOL TITLE: App-Assisted Day Reconstruction to Reduce Treatment Burden and Logistic Toxicity in Cancer Patients – Aim 1

VERSION DATE: 01/05/2023

The patient interview data will also be used to develop user stories, an approach that is widely used in agile software development to identify key app requirements and provide good business cases for these requirements. Based on the interview findings, we will develop user interface sketches and app function narratives using established usability guidelines to illustrate functionality and appearance of the app.

Surveys will be scored using standard methods. Mean scores and score distributions will be evaluated.

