### 17.2 Power Analysis:

A sample size of 20 participants will allow us to estimate the overall satisfaction rate with a margin of error of  $\pm 18\%$ .

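### Does a 5-month participation period conflict with enrolment of up to 6 months and a survey sent only after the app design?

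*Combined protocol and SAP*

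**What the plan says.** Section 8.1 gives two timing statements. For the individual: "Individual participants will participate for approximately 2 hours over a 5 month time frame". For the study: "We will enroll all participants within 6 months and anticipate all study procedures and data analysis will be completed within 24 months".

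Section 5.2 places the survey at the end of a sequence: "After the system design, the 20 interview participants will be sent a follow-up survey". Section 17.1 says what the design rests on: "Based on the interview findings, we will develop user interface sketches and app function narratives". The findings themselves come from transcribed interviews coded by two people.

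The survey carries the quantitative primary endpoint in section 3.1: "The primary endpoint will be the proportion of participants who report an overall satisfaction score of 4.0 or above". Section 11.1 sets the numbers at "up to 30, 20 participants to complete interviews", and section 17.2 bases its precision statement of ±18% on all 20. Section 13.1 recognises that participants may "become too ill or die prior to completing the study".

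The protocol does not state how long transcription, coding and design take, on what date or in what window the survey is sent, whether the 5 months start at consent or at interview, or whether design waits for the twentieth interview.

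**The concern.** On a plain reading there is one design, built from the interviews, followed by one survey to all 20 people. If so, nobody can be surveyed before the last interview has been held and turned into sketches. Someone who joins in the first weeks of a 6-month enrolment would then wait more than 6 months, although section 8.1 speaks of 5.

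The late measurement is the one that feeds the primary endpoint. Participants are on active cancer treatment when they join, and the protocol itself foresees illness and death before completion. A longer gap could plausibly mean fewer returned surveys and more raters whose treatment has ended. The margin in section 17.2 assumes 20 responses, and the surplus of consented patients covers losses before the interview, not between interview and survey. At stake would be the size and make-up of the group behind the primary proportion, and contact with people after the period they were told about.

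**Working it through.** **Inputs.** Individual period: 5 months (8.1). Actual enrolment length E: at most 6 months (8.1). Number interviewed: 20 (11.1, 17.2). Time D from last interview to survey: not in the documents, so assumed to lie between 0 and 5 months. Two further assumptions are needed: each interview follows enrolment closely, and design waits for all interviews.

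**Step 1: can the 5 months be reproduced?** Under these assumptions the first enrollee's span is E + D, so the period holds for everyone when E + D ≤ 5. The protocol gives no D and only a ceiling for E. The 5 months can therefore be neither derived nor refuted outright.

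**Step 2: how many would fall outside?** With even accrual, a participant enrolled at month t waits E + D − t months. The share waiting more than 5 months is (E + D − 5)/E, held between 0 and 1.

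| E (months) | D (months, assumed) | First enrollee's span | Share beyond 5 months |
|---|---|---|---|
| 6 | 0 | 6 | 1/6 = 17% |
| 6 | 1 | 7 | 2/6 = 33% |
| 6 | 2 | 8 | 3/6 = 50% |
| 6 | 3 | 9 | 4/6 = 67% |
| 6 | 5 | 11 | 6/6 = 100% |
| 5 | 1 | 6 | 1/5 = 20% |
| 4 | 2 | 6 | 1/4 = 25% |
| 4 | 1 | 5 | 0% |
| 3 | 2 | 5 | 0% |

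The answer runs from nobody to everybody, depending on two quantities that the protocol leaves open.

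**Step 3: what would survey losses do to the ±18%?** The half-width is z × √(p(1 − p)/n). Section 17.2 states neither the confidence level nor p. At n = 20 the figure is matched approximately by:

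- 95% confidence, p = 0.80: 1.96 × √(0.16/20) = 17.5%
- 95% confidence, p = 0.78: 18.2%
- 90% confidence, p = 0.50: 18.4%

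Suppose 15 or 16 of the 20 respond. This is an illustration, because the documents give no response rate.

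| Basis | n = 20 | n = 16 | n = 15 |
|---|---|---|---|
| 95%, p = 0.80 | 17.5% | 19.6% | 20.2% |
| 90%, p = 0.50 | 18.4% | 20.6% | 21.2% |
| 95%, p = 0.50 | 21.9% | 24.5% | 25.3% |

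Like for like, on either of the first two rows, the loss costs about 2 to 3 percentage points. A rise from about 18% to about 25% appears only if p is moved from 0.80 to 0.50 at 95% confidence. That move alone adds 21.9 − 17.5 = 4.4 points at n = 20, out of a total of 25.3 − 17.5 = 7.8 at n = 15. More than half of the apparent rise is therefore unrelated to non-response.

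**Step 4: what in the analysis uses the 5 months?** The endpoint in 3.1 is a proportion with no time limit. The survey in 5.2 is tied to an event, completion of the design, and not to a date. Section 17.1 has no visit window. No section excludes a survey returned after month 5. The 24-month total leaves 24 − 6 = 18 months after the longest permitted enrolment, so a later survey still falls inside the study. Replacing the 5 by 8 or 9 would change no estimate.

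**The case for a change.** The strongest case for a change is that the plain reading is the natural one. One survey goes to the 20 interviewees, and it concerns sketches drawn from their interviews. Nothing in the plan forces the design lag to be short: advisory board meetings are quarterly plus ad hoc, and the 24-month horizon leaves ample room. An enrolment length that the protocol permits would then break its own participation period, at the point where the primary endpoint is measured. The wording needed to mend this is cheap.

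Part of this stands. The timing statements in 8.1, 5.2 and 17.1 are not reconciled, and with a full 6-month accrual and a single design step the earliest enrollees do exceed 5 months.

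The rest does not carry. That design must wait for the last interview is an inference. Constant comparison and user stories are both compatible with starting on early interviews, although sending one survey to all 20 makes the inference reasonable. More drop-out with a longer gap is plausible, but the documents contain no rate from which to size it. An allowance for survey non-response in 17.2 is a separate matter that would arise even if everyone were surveyed inside 5 months. Being on treatment is an entry criterion and not a condition for rating the design, so an extra survey item on treatment status is a preference. Shortening enrolment would trade feasibility for conformity with a descriptive figure. Whether participants were told 5 months cannot be checked, because the consent pages are not in the material available.

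**Conclusion.** The 5-month figure is a loosely worded description of expected involvement, and no change to the plan is called for. It can fail: under even accrual over the full 6 months, with design waiting for every interview, 17% of participants pass 5 months at no lag and 50% at an assumed 2-month lag. It can equally hold for everyone, as with 4 + 1 or 3 + 2 months of accrual and design. To say that it cannot hold goes beyond the text.

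The decisive point is that no analysis depends on it. Surveys returned after month 5 still count, and analysts will sensibly include every returned survey and report the number obtained. The documents show no effect on the primary proportion. They also give no basis for restating the ±18%, because the only available figure, 15 or 16 responders, is assumed and moves the margin by about 2 to 3 points on a like-for-like basis. This conclusion rests on reading 8.1 as descriptive, which fits the absence of any survey window elsewhere in the protocol.

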## **9.0 Study Population**

- 9.1 Inclusion Criteria:

≥18 years of age, currently receiving treatment for cancer, able to read/write/speak in English, and able to provide voluntary informed consent.

- 9.2 Exclusion criteria: Those who are currently incarcerated or have opted out of research contact within M Health Fairview system.

- 9.3 Screening: Participants will confirm their eligibility criteria via screening in-person, online (REDCap) or phone call with study coordinator.

**SOCIAL PROTOCOL (HRP-580)**

PROTOCOL TITLE: App-Assisted Day Reconstruction to Reduce Treatment Burden and Logistic Toxicity in Cancer Patients – Aim 1  
VERSION DATE: 01/05/2023

**10.0 Vulnerable Populations****10.1 Vulnerable Populations:**

Population / Group	Identify whether any of the following populations will be primary focus of the research (targeted), included but not the focus of the research or excluded from participation in the study.
Children	Excluded
Pregnant women/fetuses/neonates	included but not the focus
Prisoners	Excluded
Adults lacking capacity to consent and/or adults with diminished capacity to consent, including, but not limited to, those with acute medical conditions, psychiatric disorders, neurologic disorders, developmental disorders, and behavioral disorders	Excluded
Non-English speakers	Excluded
Those unable to read (illiterate)	Excluded
Employees of the researcher	Excluded
Students of the researcher	Excluded
Undervalued or disenfranchised social group	included but not the focus

**SOCIAL PROTOCOL (HRP-580)**

**PROTOCOL TITLE:** App-Assisted Day Reconstruction to Reduce Treatment Burden and Logistic Toxicity in Cancer Patients – Aim 1  
**VERSION DATE:** 01/05/2023

Active members of the military (service members), DoD personnel (including civilian employees)	included but not the focus
Individual or group that is approached for participation in research during a stressful situation such as emergency room setting, childbirth (labor), etc.	Excluded
Individual or group that is disadvantaged in the distribution of social goods and services such as income, housing, or healthcare.	included but not the focus
Individual or group with a serious health condition for which there are no satisfactory standard treatments.	included but not the focus
Individual or group with a fear of negative consequences for not participating in the research (e.g. institutionalization, deportation, disclosure of stigmatizing behavior).	included but not the focus
Any other circumstance/dynamic that could increase vulnerability to coercion or exploitation that might influence consent to research or decision to continue in research.	Excluded

**10.2 Additional Safeguards:**

All participants will have had a cancer diagnosis, which is a serious health condition. This study specifically aims to understand the time burdens of cancer care.

The proposed research will not specifically seek military members or DOD personnel, disadvantaged individuals or members of undervalued or disenfranchised social groups, however, if volunteers meets the inclusion criteria

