### 1.0 Objectives

1.1 Purpose: The number of new cases of cancer diagnosed in the U.S. was 1.7 million in 2017 and is expected to increase by 35% to 2.3 million in 2030[1]. Cancer treatments often create numerous logistic challenges in prioritizing and managing treatment and everyday life priorities and how these challenges affect their everyday lives and well-being (hence “logistic toxicity”). However, there are no established reliable tools to monitor patients’ logistic challenges and the associated impacts; and logistic toxicity has been largely unaddressed in cancer care delivery. Our objective is to develop the first **digital health app for cancer patients** to continuously monitor logistic toxicity in their daily lives. The app will combine **objective data** from mobile sensing with **subjective self-reported data** to form an app-assisted day reconstruction system that captures activity engagement and well-being information associated with cancer treatment-related activities and trips throughout the day.

The proposed patient monitoring app that captures logistic toxicity information on an ongoing basis will empower patients to advocate for care that better fits their life, give providers new insights into potential reasons for treatment non-adherence and nonresponse, and allow health systems to design more patient-centered care regimens.

We will use a participatory design approach to inform the design of our system, engaging an 8-member community advisory board (CAB; including 2 patients, 2 oncologists, 1 nurse, 1 patient advocate, 1 payer, and 1 hospital administrator), and performing in-depth interviews and follow-up surveys with 20 diverse patients undergoing treatment for cancer. Patients will supply examples of logistic toxicity and how they would like to measure and communicate logistic toxicity across scenarios. Follow-up surveys will ask participants to provide satisfaction ratings towards user interface sketches and app function narratives.

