## SOCIAL PROTOCOL (HRP-580)

PROTOCOL TITLE: App-Assisted Day Reconstruction to Reduce Treatment Burden and Logistic Toxicity in Cancer Patients – Aim 1

VERSION DATE: 01/05/2023

friends, employers, and healthcare payers and providers.[9-15] Further, burdens of cancer and cancer treatments disproportionately affect disadvantaged patients such as racial and ethnic minorities, and hence logistic toxicity is likely to reinforce persistent inequities in cancer care and outcomes.[16-19]

The cancer care landscape has rapidly evolved to accommodate COVID-19 precautions, transitioning toward telehealth, greater emphasis on patient self-management, and opportunities for providers to tailor treatment plans. Oncology clinical practices can potentially adopt interventions such as minimally disruptive medicine, care coordination, and telemedicine that could reduce logistic toxicity in cancer care delivery.[20, 21] However, implementing these interventions requires tools that can reliably track patients' behavior and well-being in navigating the day-to-day logistic burden of undertaking cancer treatment tasks.

2.2 Preliminary Data: The concept of logistic toxicity in cancer care is similar to the concepts described in treatment burden in chronic disease management, Burden of Treatment Theory, and the Cumulative Complexity Model.[22, 23] Within these frameworks, instruments such as the Treatment Burden Questionnaire (TBQ) and the Patient Experience with Treatment and Self-management (PETS) have been developed to collect self-reported, recall-based data on treatment burden.[24, 25] Building upon this prior research, effective monitoring of logistic toxicity needs to capture the **objective treatment workload** (i.e., activities and trips carried out by the patient for treatment purposes) as well as the **subjective effects** of that workload on well-being (i.e., including biographical, relational, and emotional effects).[3-7] Objective measures of logistic toxicity to date have relied on electronic health records (EHR) and claims data, which cover medical and pharmacy visits only and offer limited information on other important sources of logistic toxicity such as scheduling time, transportation, and wait time. Subjective measures to date are research-oriented retrospective measurements that are not timely enough to inform or help the patient.

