## SOCIAL PROTOCOL (HRP-580)

PROTOCOL TITLE: App-Assisted Day Reconstruction to Reduce Treatment Burden and Logistic Toxicity in Cancer Patients – Aim 1

VERSION DATE: 01/05/2023

and also happen to be from one of the groups checked above, they will be eligible to participate in the study.

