## 12.0 Recruitment Methods

12.1 Recruitment Process:

CAB: CAB members will be recruited by study team members directly via phone calls and emails. This will not involve recruitment of MHealth Fairview patients.

Cancer Patients: [name] and study staff will identify potentially eligible participants in the clinic and/or through BPIC, who will review the electronic medical records of patients at MHealth Fairview using inclusion criteria. Patients who have opted out of research, including being approached for new studies, will not be contacted or approached. Potential participants will be approached in the clinic before or after a scheduled appointment and/or via MyChart using Fairview Research Services.

Research activities will not impact or interfere with patient's appointment times or clinical care. They will be given time to whether they would like to participate and provided information to contacting the study coordinator at a later time/date if they want to consider further.

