18.4 Approximate number of records required for review: 3000

18.5 Please describe how you will communicate with research participants during the course of this research. Check all applicable boxes

This research involves record review only. There will be no communication with research participants.

Communication with research participants will take place in the course of treatment, through MyChart, or other similar forms of communication used with patients receiving treatment.

Communication with research participants will take place outside of treatment settings. If this box is selected, please describe the type of communication and how it will be received by participants.

Communication with participants will occur through phone calls and email based on participant preference for scheduling appointments and by email through REDCap or mail for survey completion. We will ask participants to complete an authorization to receive unsecured emails from study staff if they prefer that mode of contact.

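### The plan promises interviews with 20 diverse patients, but it neither defines diversity nor contains a selection step that would secure it

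*Combined protocol and SAP*

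**What the plan says.** Section 1.1 describes the work as "performing in-depth interviews and follow-up surveys with 20 diverse patients undergoing treatment for cancer". Section 2.1 explains why the mix matters: "burdens of cancer and cancer treatments disproportionately affect disadvantaged patients such as racial and ethnic minorities", and it expects logistic toxicity to reinforce existing inequities.

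The table in section 10.1 places undervalued or disenfranchised groups, and people disadvantaged in income, housing or healthcare, in its middle category, neither targeted nor excluded. Section 10.2 puts this into words. Besides military and defence personnel, those whom the study will not set out to find are "disadvantaged individuals or members of undervalued or disenfranchised social groups, however, if volunteers meets the inclusion criteria", and the sentence goes on: "and also happen to be from one of the groups checked above, they will be eligible to participate in the study".

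On selection, section 12.1 has BPIC staff "who will review the electronic medical records of patients at MHealth Fairview using inclusion criteria". Section 12.3 adds diagnosis and treatment within two years and no research opt-out. Contact follows two routes: "Potential participants will be approached in the clinic before or after a scheduled appointment and/or via MyChart using Fairview Research Services". Section 18.4 gives the size of the search: "Approximate number of records required for review: 3000". Section 11.1 allows up to 30 consents to reach 20 interviews. Sections 9.1 and 10.1 exclude people who do not speak English or cannot read.

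**The concern.** The objective names a property of the sample, and the background gives a reason for wanting it. The operational sections contain nothing that would produce it: no definition, no characteristics to vary on, no minimum numbers, and no rule for choosing at most 30 people to consent from about 3000 records. The one sentence on whether disadvantaged groups are sought says that they are not.

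This bears on the primary interview outcome. Under section 17.1 the themes, the activity and trip classification and the user stories are built from the transcripts, and the interface sketches follow from those. A burden that no interviewee raises has no direct way into that chain. The follow-up survey is unlikely to reveal the gap, because under section 5.2 the same 20 people rate the sketches.

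**Working it through.** **The plan's own figure.** The plan gives no figure for sample mix. Its only statistical figure is the ±18% margin for the satisfaction rate in section 17.2. That can be reproduced as 1.96 × √(0.8 × 0.2 / 20) = 17.5% or as 1.645 × √(0.5 × 0.5 / 20) = 18.4%; the confidence level and rate are assumptions in both. It measures precision for a proportion and says nothing about who is interviewed.

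**Where diversity could be secured, section by section.**

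- 9.1 and 9.2: age, current treatment, English, consent, incarceration and opt-out. No variation rule.
- 10.1 and 10.2: disadvantaged groups are eligible but not sought.
- 11.1: counts only.
- 12.1 and 12.3: a query on eligibility and opt-out, then a clinic or MyChart approach. No order or selection rule.
- 17.1: coding of transcripts. Describing or checking the mix of interviewees is not mentioned.

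**How likely a gap is.** Inputs: n = 20 interviews (sections 1.1 and 11.1), and q, the share of a given group among recruits. The documents do not give q, so a range is assumed. Recruits are treated as independent draws with no targeting.

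- No interviewee from the group: (1 − q)^20
- At most one: (1 − q)^20 + 20q(1 − q)^19
- Fewer than three: the same sum plus 190q²(1 − q)^18

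| Assumed q | Expected number (20q) | None | At most one | Fewer than three |
|---|---|---|---|---|
| 5% | 1 | 0.95^20 = 36% | 74% | 92% |
| 10% | 2 | 0.90^20 = 12% | 39% | 68% |
| 15% | 3 | 0.85^20 = 4% | 18% | 40% |
| 20% | 4 | 0.80^20 = 1% | 7% | 21% |
| 30% | 6 | 0.70^20 = 0.1% | – | 4% |

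For the chance of complete absence to be 5% or less, q must be at least 1 − 0.05^(1/20) = 0.139, or about 14% of recruits.

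**If interviews are lost.** Section 5.2 allows the first five interviews to be set aside as pilot data and does not say whether they would be replaced. If they are not, n = 15 and the chance of none is (1 − q)^15: 46%, 21%, 9% and 4% for q of 5%, 10%, 15% and 20%.

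Here q is the share among people who take part. If a group accepts invitations less often than others, its q is below its share of the clinic population.

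**The case against.** The strongest reply is that section 10.2 is safeguard text. It restates the choice made in the vulnerable-populations table, and saying that a vulnerable group is not targeted does not forbid interviewing a varied sample. This stands. A reader might infer that 10.2 lays down a rule opposite to the objective, but that requires *diverse* in 1.1 to mean social disadvantage. Section 1.1 does not say so; age, cancer type or treatment would also fit. The supportable defect is an undefined term with no step behind it. It remains a defect because no step secures variation in age, cancer type or treatment either.

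A reader might also infer that the study takes the first 20 volunteers, or that patients with few clinic visits are the least likely to be approached. The documents support neither. No order of enrolment is stated, up to 30 may consent, and the record query and MyChart route do not depend on visit frequency. The split between routes is not given.

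The size of the risk is also open to challenge. Complete absence is unlikely for a group at 20% or more of recruits, and disadvantage as worded in 10.1 is broad enough to reach such a share. That stands, and it limits the point to smaller groups.

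Finally, this is formative qualitative work that need not be statistically representative, and an advisory board of eight, two of them patients, gives input throughout. Both are true. But the request is for variation, which the plan itself promises, and the board does not replace the interviews from which the classification and user stories are derived.

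**Conclusion.** The point holds as a gap between a stated property of the sample and the procedures meant to deliver it. Nothing in the plan secures the diversity promised in 1.1, and 10.2 needs to be reconciled with that promise.

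The size depends on group shares that the documents do not give. Under the assumed shares, the chance of missing a group entirely is substantial at 5% to 10% of recruits (36% to 12%), small at 15% (4%) and about 1% at 20%. Thin representation reaches further: at 15% there is still a 40% chance of fewer than three interviewees. The calculation assumes independent recruitment without targeting.

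It would go too far to conclude that disadvantaged patients will be absent, since they are eligible, or that their burdens cannot appear in the results, since other interviewees may report the same ones. Nor does the gap invalidate the endpoints. It limits how far the themes, user stories and satisfaction result can be carried beyond the people interviewed. The change is worth making because a better method is available at the same 20 interviews.

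**What to change.** 1. In 1.1, define *diverse* on a few named characteristics, for example race/ethnicity, one marker of disadvantage, and clinic-administered versus home or oral treatment.
2. In 12.1 and 12.3, add a purposive (maximum-variation) rule with small minimum counts per characteristic within the same 20 interviews. Invite from the planned record query by unfilled characteristic first.
3. Before adopting this, confirm that the query can return those fields; the plan describes it only in terms of eligibility and opt-out. The ancillary review checklist answers no to using BPIC data, while 12.1, 12.3 and 18.3 rely on BPIC. Reconcile these at the same time.
4. Reword 10.1 and 10.2 so that seeking variation is consistent with the voluntary-consent safeguards, which stay unchanged.
5. Report the achieved mix with the themes and the satisfaction result.

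The cost is a protocol amendment and somewhat slower accrual for the last unfilled characteristics within the 6-month enrolment window of section 8.1. The number of interviews does not change. If an unfilled cell is released at a set date to protect accrual, some risk remains. Minimum counts also do not reach the excluded patients who do not speak English or cannot read; state this as a limitation.

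If purposive selection is not adopted, drop *diverse* from 1.1 and limit the conclusions to the patients actually interviewed.
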